### 11.3 Procedures for Recording and Reporting

AEs are collected from the time of informed consent. Any preexisting medical conditions or signs/symptoms present in a subject prior to the start of the study (i.e., before informed consent is signed) are not considered AEs in the study and should be recorded in the medical history section of the eCRF.

In addition, temporary lens awareness or visual changes during the fitting process are not considered AEs if the Investigator assesses that the symptom(s) can reasonably resolve within the anticipated adaptation period.

For each recorded event, the ADEs and SAEs documentation must include: date of occurrence, severity, treatment (if applicable), outcome, and assessments of the seriousness and causality. In addition, the Investigator must document all device deficiencies reported or observed with test and control products on the device deficiency eCRF. The site must submit all available information on ADEs, SAEs, and device deficiencies to the study sponsor immediately as follows:

- ADEs or SAEs are documented on the *Serious Adverse Event and Adverse Device Effect* eCRF within 24 hours of the Investigator's or site's awareness.
- Device deficiencies are documented on the *Device Deficiency* eCRF within 24 hours of the Investigator's or site's awareness.
- Additional relevant information after initial reporting must be entered into the eCRF as soon as the data become available.
- Document any changes to concomitant medications on the appropriate eCRFs.
- Document all relevant information from Discharge Summary, Autopsy Report,
- Certificate of Death etc., if applicable, in narrative section of the *Serious Adverse Event and Adverse Device Effect* eCRF.

*Note:* Should the EDC system become non-operational, the site must complete the appropriate paper *Serious Adverse Event and Adverse Device Effect* and/or *Device Deficiency* Form. The completed form is emailed to the Study Sponsor at [[contact]](mailto:[contact]) according to the timelines outlined above; however, the reported information must be entered into the EDC system once it becomes operational.

Study Sponsor representatives may be contacted for any protocol related question and their contact information is provided in the Manual of Procedures that accompanies this protocol.

Further, depending upon the nature of the AE or device deficiency being reported, the Study Sponsor may request copies of applicable portions of the subject's medical records. The Investigator must also report all AEs and device deficiencies that could have led to a SADE according to the requirements of regulatory authorities or IRB/IEC.

### **Intensity and Causality Assessments**

Where appropriate, the Investigator must assess the intensity (severity) of the AE based on medical judgment with consideration of any subjective symptom(s), as defined below:

#### ***Intensity (Severity)***

Mild	An AE is mild if the subject is aware of but can easily tolerate the sign or symptom.
Moderate	An AE is moderate if the sign or symptom results in discomfort significant enough to cause interference with the subject's usual activities.
Severe	An AE is severe if the sign or symptom is incapacitating and results in the subject's inability to work or engage in their usual activities.

For every AE in the study, the Investigator must assess the causality (Related or Not Related to the medical device or study procedure). An assessment of causality will also be performed by Study Sponsor utilizing the same definitions, as shown below:

#### ***Causality***

Related	An AE classified as related may be either definitely related or possibly related where a direct cause and effect relationship with the medical device or study procedure has not been demonstrated, but there is a reasonable possibility that the AE was caused by the medical device or study procedure.
Not Related	An AE classified as not related may either be definitely unrelated or simply unlikely to be related (i.e., there are other more likely causes for the AE).

The Study Sponsor will assess the AEs and may upgrade the Investigator's assessment of seriousness and/or causality. The Study Sponsor will notify the Investigator of any AEs that is upgraded from nonserious to serious or from unrelated to related.

## 11.4 Return Product Analysis

Study Sponsor representatives and their contact information are provided in the MOP that accompanies this protocol.

Alcon study products associated with device deficiencies and/or product related AEs should be returned and may include a PR# (if applicable), which will be provided by Study Sponsor after the case is entered in the Study Sponsor's Global Product Complaint Management System (GPCMS). Refer to the MOP for details IP return.

## 11.5 Unmasking of the Study Treatment

Masked information on the identity of the assigned medical device should not be disclosed during the study (refer to Section 9.4). If the treatment code needs to be broken in the interest of subject safety, the Investigator is encouraged to contact an appropriate Study Sponsor representative prior to unmasking the information if there is sufficient time. Dependent upon the individual circumstances (i.e., medical emergency), the code may be broken prior to contact with the Study Sponsor. The Study Sponsor must be informed of all cases in which the code was broken and of the circumstances involved. Additionally, the Study Sponsor may be required to unmask the information in order to fulfill expedited regulatory reporting requirements.

## 11.6 Follow-Up of Subjects with Adverse Events

The Investigator is responsible for adequate and safe medical care of subjects during the study and for ensuring that appropriate medical care and relevant follow-up procedures are maintained after the study.

The Investigator should provide the Study Sponsor with any new safety information (which includes new AEs and changes to previously reported AEs) that may affect the safety evaluation of the device. For AEs that are unresolved/ongoing at time of discontinuation, any additional information received at follow-up should be documented in the eCRFs up to study completion (i.e., database lock). Any additional data received up to 3 months after subject completed the study should be documented and available upon the Study Sponsor's request.

All complaints received after this time period will be considered and processed as spontaneous (following the postmarket vigilance procedures) and should be communicated to the medical device's manufacturer as per local requirements.

## 11.7 Pregnancy in the Clinical Study

Women of childbearing potential or women who are pregnant at the time of study entry are not excluded from participation. Pregnancy should be included in the pregnancy eCRF when a pregnant woman enters the study or if a woman becomes pregnant during the study.

Pregnancy is not reportable as an AE; however, complications may be reportable and will be decided on a case-by-case basis.

## 12 ANALYSIS PLAN

Continuous variables will be summarized using the number of observations, mean, SD, median, minimum, and maximum, as well as confidence intervals (CIs) or confidence limits (CLs) where applicable. Categorical variables will be summarized with frequencies and percentages from each category.

Any deviations to the analysis plan will be updated during the course of the study as part of a protocol amendment or will be detailed in the clinical study report.

### 12.1 Subject Evaluability

Final subject evaluability must be determined prior to breaking the code for masked treatment (lens sequence) assignment and locking the database, based upon the Deviations and Evaluability Plan (DEP).

### 12.2 Analysis Sets

#### 12.2.1 Safety Analysis Set

Safety analyses will be conducted using the safety analysis set on a treatment-emergent basis. As such, the safety analysis set will include all subjects/eyes exposed to any study lenses evaluated in this study. For treatment-emergent safety analyses, subjects/eyes will be categorized under the actual study lens exposed in the corresponding lens sequence.

#### 12.2.2 Full Analysis Set

The full analysis set (FAS) is the set of all randomized subjects who are exposed to any study lenses evaluated in this study.

#### 12.2.3 Per Protocol Analysis Set

The per protocol (PP) analysis set is a subset of FAS and excludes all data/subjects that have met any of the critical deviation or evaluability criteria identified in the DEP.

## 12.3 Demographic and Baseline Characteristics

Demographics and baseline information will be summarized by lens sequence and overall. Frequencies and percentages will be presented for categorical variables such as sex, age group, race, and ethnicity. Number of observations, mean, SD, median, minimum, and maximum will be presented for continuous variables such as age.

## 12.4 Effectiveness Analyses

This study [REDACTED] will use the FAS as the primary analysis set.

[REDACTED]

[REDACTED]

[REDACTED]

[REDACTED]

### 12.4.1 Analysis of Primary Effectiveness Endpoint(s)

The primary objective of this study is to demonstrate noninferiority in VA at distance when wearing [REDACTED] contact lenses compared to DT1 contact lenses, after approximately 4 days of wear.

The primary endpoint is distance VA with study lenses (dispensed power) at Day 4, collected for each eye in logMAR.

#### 12.4.1.1 Statistical Hypotheses

The null and alternative hypotheses are formulated in terms of the predefined margin of 0.05 for noninferiority:

$$H_0: \mu_{(T)} - \mu_{(C)} \geq 0.05$$

[figure not shown]
$$H_a: \mu_{(T)} - \mu_{(C)} < 0.05$$

where  $\mu_{(T)}$  and  $\mu_{(C)}$  denote the mean distance VA at Day 4 [REDACTED] on the logMAR scale.

#### 12.4.1.2 Analysis Methods

A mixed effects repeated measures model will be utilized to test these hypotheses. The model will include terms for lens, visit, lens by visit interaction, sequence, and habitual lens brand

(DT1, non-DT1). Within-subject correlation due to the contralateral design will also be accounted for in the model. Lens difference [REDACTED] and the corresponding one-sided 95% upper confidence limit will be computed at Day 4. Noninferiority in distance VA will be declared if the upper confidence limit is less than 0.05.

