BCVA with manifest refraction (OD, OS, logMAR distance)	X	(X)	(X)	(X)
Biomicroscopy	X	X	X	(X)

Procedure / Assessment	Visit 1 Screening / Baseline / Dispense	Visit 2 Day 4 Follow- up / Exit	Early Exit	Unscheduled Visit
	Day 1	Day 4 (-1/+1 Day)	N/A	N/A
Determine and record study lenses power (dispensed power, OD, OS)	X			
VA with study lenses (dispensed power) (OD, OS, logMAR distance)	X	X	(X)	(X)

Procedure / Assessment	Visit 1 Screening / Baseline / Dispense	Visit 2 Day 4 Follow- up / Exit	Early Exit	Unscheduled Visit
	Day 1	Day 4 (-1/+1 Day)	N/A	N/A
Unplanned lens replacement with reason		(X)		(X)
AEs	X	X	X	X
Device deficiencies	X	X	X	X
Exit Form	(X)	X	X	(X)

(X) Assessment performed as necessary, e.g., decrease of VA by 2 lines or more with investigational product

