## **8 STUDY POPULATION**

The study population consists of male and female subjects ages 18 and older with normal eyes (other than the need for optical correction for myopia) and who are successful spherical soft contact lens wearers in both eyes for a minimum of 5 days per week and 10 hours per day during the past 3 months. The eligible study population will be representative of the investigational product target population.

The aim is to enroll (consent) approximately 110 subjects at approximately 7 sites in the US, with 14 (intended minimum) to 16 (intended maximum) subjects per site, and a target of 100 total subjects completed. Site-specific targets may vary based upon individual site capabilities. [REDACTED]  
[REDACTED]  
[REDACTED]  
[REDACTED]

Estimated time needed to recruit subjects for the study is approximately 3 weeks; however, unanticipated circumstances may shorten or lengthen this time and would not require amendment of this protocol. Because a 5% screening failure rate is expected, approximately 110 subjects are targeted to be enrolled (consented).

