## 9.3 Treatment Assignment / Randomization

Qualifying subjects will be randomized in a 1:1 ratio to receive treatment (lenses) in a contralateral sequence.

Sequence	EDC/randomization integration system	
Sequence 1	LID220365(OD)/LID006961(OS)	
Sequence 2	LID006961(OD)/LID220365(OS)	

Only after signing the ICF, a subject will be assigned a subject number by the electronic data capture system.

[figure not shown]
A randomization list will be generated using a validated system that automates the random assignment of treatment (lens sequence) to randomization numbers in the specified ratio. Subjects will be assigned treatment (lens sequence) according to the randomization list uploaded in the EDC/randomization integration system. The randomization list will be generated and maintained by the study sponsor.

At Visit 1, all eligible subjects will be randomized via the EDC/randomization integration system to one of the treatments (lens sequences). The investigator or delegate will access the respective system after confirming that the subject meets all the eligibility criteria. A randomization number will be automatically assigned to the subject according to the subject randomization list but will not be communicated to the site user. The EDC/randomization integration system will inform the site user of the treatment (lens sequence) assignment to be dispensed to the subject.

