1.3 Randomization

A member of the Randomization Programming group at Alcon who is not part of the study team will generate the randomized allocation schedule(s) for study lens sequence assignment. Randomization will be implemented in the Electronic Data Capture (EDC)/randomization integration system.

Qualifying subjects will be randomized in a 1:1 ratio to receive treatment (lens) in contralateral sequence [REDACTED]

Sequence	EDC/randomization integration system	[REDACTED]
Sequence 1	LID220365(OD)/LID006961(OS)	[REDACTED]
Sequence 2	LID006961(OD)/LID220365(OS)	[REDACTED]

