4 EFFECTIVENESS ANALYSIS STRATEGY

This study [REDACTED]
[REDACTED] will use the FAS as the primary analysis.

[REDACTED]
[REDACTED]
[REDACTED]

[REDACTED]

Continuous variables will be summarized using the number of observations, mean, SD, median, minimum, and maximum, as well as confidence intervals (CIs) or confidence limits (CLs) where applicable. Categorical variables will be summarized with frequencies and percentages from each category.

All data obtained in evaluable subjects/eyes will be included in the analysis. No imputation for missing values will be carried out for the effectiveness analyses.

[figure not shown]
For all planned inferential analyses, alternative models/methods may be considered, for instance, if convergence cannot be achieved.

A listing of select effectiveness data will also be provided.

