4.3 Statistical Methods for Effectiveness Analyses

4.3.1 Primary Effectiveness Analysis

A mixed effects repeated measures model will be utilized to test these hypotheses. The model will include terms for lens, visit, lens by visit interaction, sequence, and habitual lens brand stratum (DT1, non-DT1). Within-subject correlation due to the contralateral design will also be accounted for in the model. Lens difference [REDACTED] and the corresponding one-sided 95% upper confidence limit will be computed at Day 4. Noninferiority in distance VA will be declared if the upper confidence limit is less than 0.05.

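### The primary visual acuity model has no eye (OD/OS) term and names no covariance structure; specifying both is a cheap improvement, not a correction of the decision rule

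*Protocol*

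**What the plan says.** Protocol 12.4.1.2 specifies the primary analysis as a mixed effects repeated measures model: "The model will include terms for lens, visit, lens by visit interaction, sequence, and habitual lens brand". SAP 4.3.1 gives the same list and calls habitual brand a stratum. Eye appears in neither list, and the sentence giving the terms is not redacted in either document.

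On dependence between measurements, both documents say only: "Within-subject correlation due to the contralateral design will also be accounted for in the model". The visible text names no structure. SAP section 4 adds that "alternative models/methods may be considered, for instance, if convergence cannot be achieved", without naming the alternative.

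On the design, Protocol 9.3 states: "Qualifying subjects will be randomized in a 1:1 ratio to receive treatment (lenses) in a contralateral sequence". Sequence 1 puts the test lens on the right eye and the comparator on the left; sequence 2 is the reverse. Protocol Table 3-1 schedules study-lens acuity for each eye at Visit 1 and at Day 4, so each subject contributes four values. Noninferiority is declared if the one-sided 95% upper limit for the Day 4 lens difference is below 0.05 logMAR. That rule is the same in both documents.

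**The concern.** Eye is the factor that the randomisation balances against lens, and the model does not use it. The sequence term looks as though it might do the job, but it compares subjects with subjects. Within a subject it cancels from the test-minus-comparator difference, as does brand. Eye is the lens-by-sequence interaction, which is not in the model. A mean OD-OS difference therefore stays in the paired differences, positive in one sequence and negative in the other. It adds variance and, if the analysed sequences are unequal, moves the estimate.

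The unnamed covariance bears on the remedy. Eye terms help only if the model gives the right variance for the Day 4 paired difference. A subject random intercept alone does not do so if eyes keep individual deviations across the two visits. This analysis is the trial's only success criterion, so these choices are better settled before unmasking.

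**Working it through.** **Inputs from the documents.** SD of the paired difference 0.0567, N = 10 (80% power) and N = 14 (90%), from SAP section 7; margin 0.05 and one-sided alpha 0.05; 100 completers from Protocol section 8.

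**Assumed, because the documents do not give them.** The mean OD-OS difference d; the analysed split n1:n2; the share of within-subject variance that is a persistent eye-level deviation; a true lens difference of 0 for power; and 0.0567 read as the paired SD without an eye effect. As a near-balanced case I take 52:48. The protocol says "Because a 5% screening failure rate is expected"; 110 less 5% is about 104 randomised, of whom 100 complete.

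**The plan's own figures.** For a one-sided paired t-test with true difference 0, power is 0.779 at N = 9 and 0.823 at N = 10, which reproduces the stated 10. For 90%, N = 13 gives 0.911 and the stated 14 gives 0.930, as if rounded up to an even number. With an eye term (N - 2 error df), power is 0.815 at N = 10 and 0.928 at N = 14, so the stated sizes still suffice.

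**Effect of omitting eye.** Let D be test minus comparator at Day 4, with true lens difference delta. Its mean is delta + d in sequence 1 and delta - d in sequence 2.

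- Shift of the estimate: d(n1 - n2)/n.
- SD of D at 50:50 without eye: sqrt(0.0567² + d²).
- Half-width: t(0.95, 99 df) × SD/sqrt(100) = 1.6604 × SD/10. With eye this is 0.0094.

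| d (logMAR) | SD without eye | SE ratio, without/with eye | Half-width without eye | Shift at 52:48 | Shift at 55:45 |
|---|---|---|---|---|---|
| 0.005 | 0.0569 | 1.004 | 0.0095 | 0.0002 | 0.0005 |
| 0.01 | 0.0576 | 1.015 | 0.0096 | 0.0004 | 0.001 |
| 0.02 | 0.0601 | 1.060 | 0.0100 | 0.0008 | 0.002 |
| 0.03 | 0.0641 | 1.131 | 0.0107 | 0.0012 | 0.003 |

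**One-sided error at a true difference of 0.05, unstructured covariance.** Simulation with two eyes, two visits, N = 100 and share 0.5:

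- At 50:50, for d = 0.01, 0.02 and 0.03: 4.8%, 4.5% and 3.1% without eye terms; 5.2%, 5.1% and 5.0% with them.
- At d = 0.02 without eye terms: 3.1% at 52:48, 5.4% at 48:52, 2.0% at 55:45 and 8.2% at 45:55. With eye terms: 5.0% at both 48:52 and 45:55.
- Averaged over simple randomisation, analysing the Day 4 paired difference directly, the rate without eye is 4.9% to 5.1%. The figures above are conditional on the split.

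**Subject random intercept only.** The four values give three within-subject contrasts: the two paired lens differences (one per visit) and the visit contrast. Scaled alike, the first two have variance s² and the third has s²(1 - share) if there is no subject-by-visit variance. The model pools them to s²(1 - share/3), so the Day 4 SE is multiplied by sqrt(1 - share/3). At shares 0.3, 0.5 and 0.7 this is 0.95, 0.91 and 0.88, giving half-widths of 0.0089, 0.0086 and 0.0082 with the same t quantile. For d = 0.01 to 0.03 at 50:50, simulated error is:

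- share 0.5: 6.4% to 4.9% without eye terms, 6.6% to 6.8% with them;
- share 0.7: 7.1% to 5.5% without, 7.4% to 7.6% with.

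Eye terms therefore do not repair a short SE; they remove the extra variance that partly hid it. Subject-by-visit variance adds twice its value to the visit contrast. At half the eye-level variance all three contrasts have variance s², and the SE is no longer too small (at share 0.5 and d = 0.01: 4.7% without eye terms, 5.1% with).

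**Power.** At 100 completers and a true difference of 0, power exceeds 99.9% for d up to 0.03, with or without eye terms.

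**The case against.** The strongest reply is that nothing here is an error. The estimate is unbiased over the randomisation, the average error rate is nominal, and N = 10 would suffice where 100 are planned. All of that stands, and it is why this is an optional improvement.

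No value of d is given, and nothing in the documents suggests 0.02 to 0.03; at 0.01 or below the widening is at most 1.5%. The SAP labels 0.0567 as the overall SD of the paired difference, so it may already contain any eye effect. In that case nothing is lost against plan, and the eye term could only gain. Both points stand, so the larger percentages show a range and are not predictions.

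The 8.2% needs both d = 0.02 and a 45:55 split in the unfavourable direction; the mirror split gives 2.0%. Details of the randomisation are not visible, so the chance of such a split cannot be judged.

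Neither document says that a lone subject intercept will be fitted. That too stands: those error rates describe a model that the wording permits, not one that it announces.

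Finally, results depend somewhat on how the covariance is indexed. At d = 0.02 and 50:50, analysing the Day 4 paired difference directly gives about 4% error without eye, against 4.5% with covariance indexed by eye. The difference is small and does not alter the conclusion. Indexing by eye remains valid if the two lenses have different variances, because OD minus OS and test minus comparator differ only in sign.

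**Conclusion.** The point holds as a low-priority improvement. The model leaves out a factor that the design randomises, and neither sequence nor brand can stand in for it. With balanced sequences and a correct covariance, the cost is a half-width 0.4% to 13.1% wider for d of 0.005 to 0.03. With unequal sequences there is also a chance shift of up to 0.0012 at 52:48 or 0.003 at 55:45 for d up to 0.03. The covariance matters at least as much: an intercept-only model could understate the SE by about 5% to 12% at shares 0.3 to 0.7, provided subject-by-visit variance is small. All of this rests on assumed values of d, the split and the share. In every case considered the half-width is near 0.01 against a margin of 0.05, so the noninferiority conclusion is very unlikely to change. The hypotheses, confidence limit and decision rule are sound.

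**What to change.** In Protocol 12.4.1.2 and SAP 4.3.1, state the model in full:

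- **Fixed effects:** lens, visit, lens-by-visit, eye (OD, OS), eye-by-visit, sequence and habitual lens brand.
- **Covariance:** unstructured within subject over the four eye-by-visit measurements (OD and OS at Day 1 and Day 4).
- **Fallback if the fit does not converge:** random effects for subject, eye within subject, and subject-by-visit, replacing the open-ended wording in SAP section 4 for this analysis.

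The eye terms should not be added to a model with only a subject random intercept.

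The cost is one sentence in each document and no new data. The eye terms use 2 degrees of freedom, and the covariance has 10 parameters (4 variances and 6 covariances), estimated from about 100 subjects with four values each. If there is no eye effect, the SE is multiplied by n/(2 sqrt(n1 n2)). That is a rise of 0.08% at 52:48 and about 0.5% at 55:45 (0.00567 to 0.00570), and essentially nothing when balanced.
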